7.3 Derived and Computed Variables

The following derived and computed variables have been initially identified as important for the statistical analysis. Additional variables may be required. The SAP will not be amended for additional variables that are not related to the primary target or key secondary target variables. Any additional derived or computed variables will be identified and documented in the SAS programs that create the analysis files. If the SAP is not amended, further derivations related to primary and secondary target variables will be described in the CSR.

7.3.1 Baseline Variables

Table 1 shows the variables, which will be calculated for the analysis of subject disposition and baseline characteristics and to define subgroups based on baseline characteristics.

Table 1: Derived Subject Disposition and Baseline Variables

Data	Variable	Derivation
Disposition	time on study [months]	Time on study will be calculated as time from Cycle 1 Day 1 until date of last visit or date of study completion whichever is later [= (date of last visit/study completion – Cycle 1 Day 1 + 1)/ XXXXXXXXXX]
	Time since first diagnosis of multiple myeloma [months]	Time since first diagnosis will be calculated as time from date of first diagnosis until Cycle 1 Day 1. If date of diagnosis is incomplete, time since first diagnosis [months] will be calculated based on the latest possible date for date of diagnosis.
Previous Drug Treatment of MM	Refractory to previous drug treatment [Yes/no/missing]	Progression of disease while on a specific therapy, or within 60 days of completion of a given therapy. (S. Lonial, Hematology 2010) [4] In case of incomplete dates mid of month (15 th)/ mid of year (30JUN) will be used for date of end of previous therapy and/or date of progression. Each previous drug treatment of 1 therapy line should have the same date of progression. In

		
case date of progression is missing for a treatment or different dates are entered, the latest date of progression will be used for all treatments of this therapy line.
 
In case date of progression or date of end of previous therapy is completely missing or progression status is not determined at all for previous therapies (e.g. subjects enrolled at the beginning of the study), variable will be missing
 
This variable will be determined for each previous drug treatment.

	Refractory to most recent previous drug treatment line [Yes/no/missing]	
The most recent drug treatment will be selected based on most recent end date. Refractory will be determined as described above.
 
This variable will be determined per subject.

	Double-Refractory to previous drug treatments containing a proteasome inhibitor and IMiD [Yes/no/missing]	
Refractory to a proteasome inhibitor and refractory to an IMiD.
 
Refractory will be determined as described above.

Cytogenetics of MM Cells (Bone Marrow)	high risk evaluation [Yes/no/missing]	
Reference: Chng et al., Leukemia, 2014 [5]
 
high risk is met [Yes] if a subject has
 
(1) chromosomal aberration t(4;14) or Del17p13and
 
(2) International Staging System (ISS) criteria II/III
 
In case chromosomal aberrations and/or ISS are not determined or one chromosomal aberration is missing and the other one is absent, variable will be missing.

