7.4 Subgroups Used for Efficacy Analysis

For efficacy analyses the following subgroups will be defined:

- Age: < 65 years / ≥ 65 years
- Age: ≤ 75 years / > 75 years
- Prior therapy lines: ≤ median / > median (Note: median will be determined in total safety population)
- High risk cytogenetics: Yes / No
- Sex: Male / Female
- ISS: I or II / III
- Percentage of plasma cells in bone marrow at screening: < 60 / ≥ 60
- Subjects refractory to
 - Proteasome inhibitors (PIs) and Immunomodulatory Drugs (IMiDs)
 - any IMiDs only (not refractory to any PIs, but allowed to be refractory to any other previous drug)
 - any PIs only (not refractory to any IMiDs, but allowed to be refractory to any other previous drug)

- last prior treatment line Yes / No
- any prior treatment line Yes / No

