Moreover the number of previous lines of therapy (as entered into the eCRF) will be summarized descriptively (summary statistics and frequency table). The frequency table will contain cumulative subcategories, i.e. number of subjects with $\geq x$ prior therapy lines, for all possible numbers x .

Best response under treatment and type of progression associated with each previous drug treatment will be included in listings.

Moreover, it will be determined for each previous drug treatment if the subject was refractory to the treatment (see section 7.3.1).

Incidences of previous drug treatments to which subjects were refractory will be summarized by group, subgroup and agent.

In addition, the rate of subjects who were refractory to the most recent drug treatment line and the rate of subjects who were double-refractory will be presented.

Time Since First Diagnosis of Multiple Myeloma [Months]: Time since first diagnosis will be measured from date of first diagnosis until Cycle 1 Day 1.

Cytogenetics of MM Cells (Bone Marrow): The frequency of translocations t(4;14) and t(14;16) and deletions Del13 and Del17p13 and other documented cytogenetic abnormalities (measured at screening or known from historical data) will be summarized descriptively in a frequency table (categories: yes/no/missing/not tested). Moreover, the table will contain frequencies for high risk evaluation (see section 7.3.1).

DNA Analysis of FcγRIIIa Polymorphism (Mucosal Cheek Swab): The frequency of each genotype (158FF, 158VF, 158VV, other, missing) will be summarized descriptively in a frequency table.

Concomitant Medication: All medications will be coded using the WHO Drug Dictionary (March 2011, and updated to the newest version March 2020 for the follow-up analyses). Incidences of concurrent medications will be summarized by Anatomical Therapeutic Chemical (ATC) level 2 and ATC level 4.

Concomitant medication is defined as a medication other than study drug that was administered during the treatment or follow-up period from day of first treatment up to the end of study.

Therefore entries of medications which were discontinued before start of treatment will be excluded from concomitant medication tables but will be included and flagged in the listings as previous medications.

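### When end of therapy and progression are both known only to the same calendar year, the SAP's 30 June rule labels that prior treatment refractory whatever the true interval

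*SAP*

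**What the plan says.** SAP 7.3.1, Table 1, defines the flag, separately for each previous drug treatment, as "Progression of disease while on a specific therapy, or within 60 days of completion of a given therapy". Incomplete dates are then filled in. A missing day becomes the 15th, and where the month is missing too, "mid of year (30JUN) will be used for date of end of previous therapy and/or date of progression". Drugs given in one line share one progression date; if dates are absent or differ, "the latest date of progression will be used for all treatments of this therapy line". The flag is set to missing only in a narrower situation: "In case date of progression or date of end of previous therapy is completely missing or progression status is not determined at all". A date with a year but no month is incomplete, not completely missing, so it is imputed.

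The per-treatment flag feeds a most-recent-line flag and a double-refractory flag, the latter defined as "Refractory to a proteasome inhibitor and refractory to an IMiD". SAP 8.3 tabulates refractory treatments by group, subgroup and agent, gives the most-recent-line rate, and states that "the rate of subjects who were double-refractory will be presented". SAP 7.4, under the item "Subjects refractory to", lists five groupings: both drug classes, IMiDs only, proteasome inhibitors only, last prior line, and any prior line. SAP 9.2.1 applies them to BOR, ORR, CBR, DCR and PFS, in the combined presentations only.

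**The concern.** The rule has to resolve a 60-day threshold. In a 365-day year 30 June is day 181, so a year-only date moved there can be wrong by up to 181 − 1 = 180 days one way or 365 − 181 = 184 days the other, about three times the threshold. When both dates are year-only, the recorded calendar years alone decide the label.

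Errors can spread. One false 'yes' makes the any-prior-line grouping positive. Because one progression date serves the whole line, a line containing both a proteasome inhibitor and an IMiD can produce double-refractory status from a single set of year-only dates. A false 'yes' can also move a subject out of the IMiD-only or proteasome-inhibitor-only grouping. Recommended-dose groups may hold as few as 9 subjects (Protocol 15.9, SAP 5), where one wrongly classified subject moves a baseline rate by 1/9, or 11 percentage points.

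The rule also sits awkwardly with the rest of the plan. SAP 7.1 and Protocol 15.11 say missing values are not imputed. The partial-date rules for concomitant medication (SAP 8.3) and adverse events (SAP 10.2) do not replace dates but ask what the recorded parts can definitely show. The cytogenetic risk variable in the same Table 1 becomes missing when its inputs cannot settle it.

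**Working it through.** The plan gives no figure for this point, so there is none to reproduce. The inputs are the 60-day threshold and the two imputation dates, all from SAP 7.3.1, Table 1. The label is 'yes' when imputed progression date − imputed end date ≤ 60 days; a negative gap is progression on therapy and also counts as 'yes'. Counts are for a 365-day year, and a leap year changes them only in the first decimal. Uniform dates within the year are an assumption.

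**1. Both dates year-only, same year.** Imputed gap = 30 June − 30 June = 0, so 'yes' in every case.
- Progression on or after end of therapy: possible pairs = 365 × 366 / 2 = 66,795. Pairs with a true gap of 0 to 60 days = 61 × 365 − (60 × 61)/2 = 22,265 − 1,830 = 20,435. Truly refractory = 20,435 / 66,795 = 30.6%, so 69.4% are falsely 'yes'.
- Either order possible: pairs = 365² = 133,225. Progression earlier than end of therapy = 133,225 − 66,795 = 66,430, all truly refractory. Truly refractory = (66,430 + 20,435) / 133,225 = 65.2%, so 34.8% are falsely 'yes'.

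**2. Both year-only, progression in the next year.** Imputed gap = 365 or 366 days, so 'no' in every case. Pairs truly within 60 days = 60 + 59 + … + 1 = 1,830, and 1,830 / 133,225 = 1.4% are falsely 'no'.

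**3. One date year-only, same year, progression on or after end of therapy.** There are 66,795 − 20,435 = 46,360 pairs that are truly not refractory.
- Progression year-only: 'yes' when 181 − end day ≤ 60, that is, when therapy ended on day 121 (1 May) or later. False 'no' = 120 × 61 / 20,435 = 35.8% of true 'yes'. False 'yes' = (184 × 185 / 2) / 46,360 = 36.7% of true 'no'.
- End of therapy year-only: 'yes' when progression falls by day 181 + 60 = 241. False 'no' = 124 × 61 / 20,435 = 37.0% of true 'yes'. False 'yes' = (180 × 181 / 2) / 46,360 = 35.1% of true 'no'.

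**4. Month-only dates.** Two dates in the same month are at most 30 days apart, so the imputed 'yes' is always right. Over all month-only pairs in one year, with progression on or after end of therapy, the 15th-of-month rule gives a false 'yes' for about 2% of true 'no' and a false 'no' for about 18% of true 'yes'.

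**5. Net direction when both dates are year-only.** Assume an end date uniform over the year and an exponential gap after it (so no progression on therapy). The share labelled refractory is then the average, over end dates, of the probability that progression falls in the same calendar year.

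| Median gap | Truly refractory | Labelled refractory |
|---|---|---|
| 2 months | 50.1% | 76.5% |
| 6 months | 20.7% | 46.0% |
| 12 months | 10.9% | 27.9% |
| 24 months | 5.6% | 15.5% |

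The net shift is upward in each scenario. About 7% to 8% of true 'yes' records are lost to 'no'.

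**The case against.** The strongest reply is that the rule may rarely bite. Protocol 9.4 and 11.4.2 ask for therapy end and progression dates, and neither document reports how many are year-only. A reader might infer that the refractory subgroups are in fact distorted; without that count the documents do not support it, and the effect could be nil. Nor do they support the inference that older therapy lines are the ones with year-only dates.

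A reader might also take 70% as the error rate. That figure excludes everyone who progressed on therapy, all of whom are refractory by definition. Admitting either order halves it, and it would fall further if treatment usually stops at or near progression. It is also a rate per treatment record. A subject may already be refractory through a fully dated line, so it does not carry over to the double-refractory or any-line rates.

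The adjacent-year 'no' might look like an equal fault, but under uniform dates it is right in about 98.6% of pairs. In Part D, Protocol 8.2.3 requires progression during or within 60 days of the last prior therapy, so a false 'yes' for the last line is unlikely there. A specific derivation may also legitimately override a general no-imputation statement, and SAP 7.1 lists all eCRF data by subject, so recorded dates can be checked.

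All of this stands and limits the size of the point. It leaves the same-year case untouched: the answer there does not depend on the interval, and the readable text of the SAP describes no undetermined category, imputation flag or sensitivity analysis for it.

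**Conclusion.** The point holds for a defined set of records. Where both dates are year-only in the same year, the imputation alone produces 'refractory', and under uniform dates about 35% to 70% of such labels would be false, depending on whether progression on therapy is allowed for. Same-year records with one year-only date can err in both directions.

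The reach is narrow: the refractory and double-refractory baseline summaries, and the five refractory groupings in descriptive subgroup tables. A reader might infer that the main conclusions are at risk. They are not: the DLT and MTD assessment, adverse events, immunogenicity, and overall ORR and PFS do not use this flag. It is an inexpensive improvement to a derivation, and its practical size depends on a count of year-only dates that the documents do not give.

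**What to change.** In SAP 7.3.1, Table 1, replace the imputation for this variable with bounds. From the recorded date parts, derive the smallest and largest possible gap between end of therapy and progression. Set 'yes' if the gap is always 60 days or less (including progression on therapy), 'no' if it is always more than 60 days, and otherwise 'missing'. Use neither 30 June nor the 15th when the possible gaps straddle 60 days.

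In practice:
- Both year-only, same year: −364 to +364 days, so missing.
- Both year-only, adjacent years: 1 to about 730 days, so missing.
- Both year-only, two or more years apart: at least 366 days, so 'no'.
- Both month-only, same month: at most 30 days, so 'yes'.

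Let the most-recent-line, double-refractory and any-line flags become missing only where an undetermined record could change the subject's answer. State how many records are undetermined, and note the rule alongside the no-imputation statement in SAP 7.1.

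The cost is a small programming change and some additional missing values in already small subgroups, including adjacent-year pairs for which 'no' would usually have been right. If that loss matters, show the affected rates with all undetermined records taken first as 'yes' and then as 'no'. The 'missing' category already exists, so no new category is needed.

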7.3.2 Immunogenicity

Subject has positive anti-MOR03087 antibodies (yes/no/missing) by visit:

- yes, if a titer is available (in this case the sample is confirmed positive)
- no, if result is reported as negative
- missing, if anti-MOR03087 measurement is not available

Subject has developed positive anti-MOR03087 antibodies during study

(yes/no/transient/not evaluable/missing):

- yes, if the subject has at least 1 confirmed positive post-baseline sample containing anti-MOR03087 antibodies including the last sample analyzed; baseline sample has to be tested negative
- no, if baseline as well as all post-baseline results are negative
- transient, if the subject has at least 1 confirmed positive post-baseline sample containing anti-MOR03087 antibodies but a negative result for the last sample analyzed; baseline sample has to be tested negative
- not evaluable, if the baseline sample of the respective subject was tested positive
- missing, if no post-baseline anti-MOR03087 measurement is available

Time to development of anti-MOR03087 antibodies [months]: Time to development of anti-MOR03087 antibodies will be defined as time from Cycle 1, Day 1 until Date of first blood sample containing anti-MOR03087 antibodies. Subjects who do not develop any antibodies by end of study will be considered as censored at the date of last blood sample taken for MOR03087 antibody analysis.

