## **15.3 ImmunogenicityAnalysis**

One of the primary objectives will be to evaluate the immunogenicity of MOR03087 in the Evaluable Population and the Safety Population. This analysis will be based on both absolute (number and percentage of subjects who develop anti-MOR03087 antibodies) and semi-quantitative (anti-MOR03087 antibody titer determination of confirmed positive samples) assessments.

The number and percentage of subjects who develop confirmed anti-MOR03087 antibodies will be summarized descriptively by treatment arm and dose level. Exact 95% confidence intervals will be provided for the rate of subjects who developed anti-MOR03087 antibodies in the recommended dose group of each treatment arm.

Time to development of anti-MOR0387 antibodies will be summarized descriptively by treatment arm and dose level using Kaplan-Meier estimates for the median, 25% quartile, and 75% quartile. If only a few subjects develop anti-MOR03087 antibodies, quantitative assessments will only be presented in listings. Otherwise, summary tables will also be provided.

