2.2 Safety, Efficacy, and Pharmacokinetic/Pharmacodynamic Endpoints

2.2.1 Primary Endpoints

The primary endpoints are

1. Determination of the MTD and/or recommended dose of MOR03087 as monotherapy, in combination with DEX, and in combination with POM + DEX and LEN + DEX
2. Determination of the recommended dosing regimen of MOR03087
3. Incidence and severity of adverse events (AEs)
4. Immunogenicity of MOR03087 based on both absolute (number and percentage of subjects who develop anti-MOR03087 antibodies) and semi-quantitative (anti-MOR03087 antibody titer determination of confirmed positive samples) assessments

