9.1 Immunogenicity Analysis

One of the primary endpoints is to evaluate the immunogenicity of MOR03087 in the Safety Population. Anti-MOR03087 antibodies will be determined by a central laboratory. The analysis will be based on both absolute numbers (number and percentage of subjects who develop anti-MOR03087 antibodies) and semiquantitative assessments (anti-MOR03087 antibody titer determination of confirmed positive samples).

The number and percentage of subjects who developed confirmed anti-MOR03087 antibodies during the study will be summarized descriptively. Rates will be calculated with respect to all subjects in the analysis group.

Exact 95%-confidence intervals will be provided for the rate of subjects who developed anti MOR03087 antibodies in combined presentations (see section 7.2).

Time to development of anti-MOR03087 antibodies [months] will be summarised descriptively using Kaplan-Meier estimates for the median, 25% quantile, and 75% quantile. 95%-confidence intervals for median, 25% quantile and 75% quantile will be provided in combined presentations.

Moreover the percentage of subjects having developed antibodies after 2, 4 and 6 months together with the corresponding 95%-confidence intervals will be estimated from the Kaplan-Meier curve for combined data.

Kaplan-Meier plots for time to development of anti-MOR03087 antibodies [months] will be provided for combined data.

Exact 95% confidence intervals and Kaplan-Meier analyses will not be produced if only very few subjects develop anti MOR03087 antibodies.

Also, if only a few subjects develop anti MOR03087 antibodies, quantitative assessments will only be presented in listings. Otherwise, summary tables may be added.

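### The SAP does not say whether transient antibody responses count in the primary immunogenicity rate, divides by subjects who cannot be assessed, and uses a different event in the Kaplan-Meier analysis

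*SAP*

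**What the plan says.** SAP 2.2.1 lists immunogenicity as a primary endpoint, measured in part by the "number and percentage of subjects who develop anti-MOR03087 antibodies". Protocol 15.3 describes the same rate: "The number and percentage of subjects who develop confirmed anti-MOR03087 antibodies will be summarized descriptively by treatment arm and dose level". Neither text requires the antibodies to persist.

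SAP 7.3.2 turns this into one variable per subject with the values "yes/no/transient/not evaluable/missing". *Yes* needs a negative baseline and a confirmed post-baseline positive, and the last sample analysed must be positive. The other relevant values are:

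- "transient, if the subject has at least 1 confirmed positive post-baseline sample containing anti-MOR03087 antibodies but a negative result for the last sample analyzed"
- "not evaluable, if the baseline sample of the respective subject was tested positive"
- *missing*, for a subject with no post-baseline measurement.

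SAP 9.1 then reports how many subjects developed confirmed antibodies, without naming the values that make up that count. It does state the denominator: "Rates will be calculated with respect to all subjects in the analysis group". The analysis set is the Safety Population, for which one dose is enough. Exact 95% confidence intervals are planned for combined presentations.

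The time-to-development variable in SAP 7.3.2 runs from Cycle 1 Day 1 to the "Date of first blood sample containing anti-MOR03087 antibodies". Only subjects who never develop antibodies are censored.

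**The concern.** A subject with a negative baseline and a confirmed positive sample during the study has developed antibodies in the sense of the endpoint. The derived variable asks whether the subject developed antibodies and gives this subject an answer other than *yes* if the final sample is negative. Two programmers could therefore produce different primary rates from the same data, and the one who follows the variable most literally leaves out confirmed seroconverters.

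The denominator can only push in one direction. Subjects without a post-baseline sample and subjects positive at baseline cannot be *yes* or *transient*, so each of them lowers the percentage. Counting missing as non-response is cautious for an efficacy rate. For an unwanted outcome the same convention is favourable to the drug.

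The Kaplan-Meier analysis addresses the same question with a different event and different subjects. Transient subjects are events there. Baseline-positive subjects, whom the rate calls not evaluable, are not excluded.

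**Working it through.** **1. The plan's own figures.** The documents give no expected antibody rate or precision. The only sizing figures, in Protocol 15.9, concern adverse events in the minimum recommended-dose group of 9. They use P(at least one) = 1 − (1 − p)^9:

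- p = 0.17: 1 − 0.83^9 = 81.3% (stated 81%)
- p = 0.23: 1 − 0.77^9 = 90.5% (stated 90%)

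Both reproduce. From this section I use only the group size of 9, which SAP 5 repeats. All subject counts below are assumptions.

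**2. Method.** Rate = x/n. The exact (Clopper-Pearson) 95% limits are the 2.5% quantile of Beta(x, n − x + 1) and the 97.5% quantile of Beta(x + 1, n − x).

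**3. Group of 9, assuming 1 *yes*, 1 *transient*, 1 *missing*, 6 *no*.**

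| Numerator | Denominator | Rate | Exact 95% CI |
|---|---|---|---|
| *yes* only | all | 1/9 = 11.1% | 0.3–48.2% |
| *yes* + *transient* | all | 2/9 = 22.2% | 2.8–60.0% |
| *yes* + *transient* | assessable, 9 − 1 = 8 | 2/8 = 25.0% | 3.2–65.1% |

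The Kaplan-Meier rule counts 2 events in these data.

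**4. Group of 18, assuming 2 *yes*, 2 *transient*, 1 *not evaluable*, 1 *missing*, 12 *no*.**

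| Numerator | Denominator | Rate | Exact 95% CI |
|---|---|---|---|
| *yes* only | all | 2/18 = 11.1% | 1.4–34.7% |
| *yes* + *transient* | all | 4/18 = 22.2% | 6.4–47.6% |
| *yes* + *transient* | assessable, 18 − 2 = 16 | 4/16 = 25.0% | 7.3–52.4% |

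**5. Denominator alone.** With *yes* as the only numerator, the 18-subject case moves from 2/18 = 11.1% to 2/16 = 12.5%. In a group of 9 with 1 *yes*, 1 *not evaluable* and 1 *missing*, the rate moves from 1/9 = 11.1% to 1/7 = 14.3%.

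**6. Kaplan-Meier on the 18-subject case at 6 months, full follow-up assumed.**

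- SAP event definition in the 16 assessable subjects: 1 − 12/16 = 25.0%.
- Baseline-positive subject added as an event at time 0 (17 subjects): 1 − 12/17 = 29.4%.
- Only *yes* subjects treated as events: 2/16 = 12.5%.

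Protocol Tables 1 and 2 schedule the baseline antibody sample at screening and none on Day 1. By the literal definition, a baseline-positive subject's first positive sample falls before Cycle 1 Day 1 and the time is negative. The SAP does not say how to handle that.

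**7. Dependence on follow-up.** SAP 4.2 allows the main analysis once all subjects have reached Cycle 3 Day 1 or end of study. SAP 4.3 plans to re-run everything later, and antibody sampling continues through later cycles and follow-up. A subject positive at the last sample before the first cut-off and negative afterwards moves from *yes* to *transient*. A count of *yes* alone can therefore fall between the two analyses, but a count of *yes* plus *transient* cannot fall for that reason.

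**8. Limiting cases.** If every positive is transient (0 *yes*, 2 *transient* of 18), a *yes*-only rate is 0% (0–18.5%) while Kaplan-Meier counts 2 events. With no transient, missing or baseline-positive subjects, all versions of the rate agree.

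**The case against.** A reader might infer that the primary rate is biased low as written. The documents do not support that. SAP 9.1 never limits the numerator to *yes*, and a transient subject literally has developed confirmed antibodies. If transients are counted, the first illustration gives 22.2% against 25.0% after the fix, and only the denominator and the baseline-positive question remain. This part of the objection stands: the numerator defect is an undefined term whose most literal coding drops seroconverters, not a demonstrated bias.

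A reader might also infer that the rate table and the curve are bound to disagree. They do so by definition only if transient subjects occur and are left out of the rate, or if baseline-positive subjects occur and enter the curve as events. The documents give no frequency for either. Crude and Kaplan-Meier estimates can also differ through censoring alone. SAP 9.1 allows the exact intervals and the Kaplan-Meier output to be dropped if very few subjects develop antibodies, without defining very few. One or two positives of 9 might fall under that rule.

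The all-subjects denominator is prespecified and follows the general rule in SAP 7.1 and the efficacy rates in SAP 9.2. No text requires an assessable-subject denominator. That makes it a declared convention, but it does not remove the downward arithmetic effect when such subjects exist.

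Finally, five tabulated values could be recombined by a reader. That is true if all five are shown, but the planned table descriptions are redacted, so the layout cannot be checked. The confidence interval would still attach to whichever rate is reported as the headline.

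**Conclusion.** The concern holds as a gap in definition. The SAP does not state whether *transient* belongs to the primary numerator, and on the natural reading of the variable it does not, although the endpoint asks only whether antibodies developed. The stated denominator keeps in subjects who cannot be counted as developing antibodies, so the rate is lowered whenever such subjects exist. The Kaplan-Meier rule treats transient subjects as events and leaves baseline-positive subjects with a time before zero.

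The size rests entirely on assumed counts. In the 9-subject illustration the rate ranges from 11.1% to 25.0% depending on the reading, with wide, overlapping intervals. The effect may be nil. This is a should-fix point: immunogenicity is a primary endpoint, but it is summarised descriptively, with no test and no decision threshold.

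**What to change.** In SAP 7.3.2 and 9.1:

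- Define the headline numerator as *yes* plus *transient*.
- Use as denominator the subjects with a negative baseline and at least one post-baseline result.
- Show persistent, transient and all-subjects percentages as supportive rows.
- Apply the same set to the Kaplan-Meier analysis, with the first confirmed post-baseline positive as the event, and list baseline-positive subjects separately.
- Assign a value to subjects with post-baseline results but no baseline result, who fit none of the five values.

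The cost is SAP wording and one table shell. No new data are needed. The reported antibody rate may come out somewhat higher.
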